### **Hypotheses**

3.1. (a) Lower testing during treatment will lead to steeper positive slopes during treatment than higher testing. The exact pattern of the treatment conditions is not predicted (e.g., low and mid better than high versus low better than mid and high versus low better than mid better than high) (b) Higher testing during treatment will lead to smaller negative slopes (i.e., less forgetting) post-treatment than lower testing. The exact pattern of the treatment conditions is not predicted (e.g., high and mid better than low versus high better than mid and low versus high better than mid better than low). 3.2. (a) Higher language (specifically vocabulary and narrative skills), working memory, and/or episodic learning scores will be associated with steeper positive slopes during treatment. (b) Better treatment learning and/or decay scores will be associated with smaller negative slopes post-treatment, indicating less forgetting. 3.3. (a) Accuracy in predicting learning outcomes will increase at each treatment point, and there will be a point during treatment when outcomes can be accurately predicted. The specific earliest point in treatment (reading 1, 2, 3, 4, or 5) when accurate predictions can be made is unknown without any specific hypothesis. (b) Accuracy in predicting retention outcomes will increase at each post-treatment point, and there will be a point during post-treatment when outcomes can be accurately predicted. The specific earliest point in post-treatment (immediate, 4-week, 8-week) when accurate predictions can be made is unknown without any specific hypothesis.

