### **Sampling Plan**

#### **Existing Data**

Registration prior to creation of data

Explanation of existing data

N/A -- Not using existing data

Data collection procedures

See attached file for details.

- [Data collection procedures.pdf](#)

Sample size

Sixty kindergarten children with DLD will participate. Children will be randomized to one of the 3 treatment manipulations (see manipulated variables) yielding 20 children per treatment condition. For each child definition and naming data will be collected for 30 treated words and 30 control words: 1 time pre-treatment, 6 times during treatment (repeated book readings 1-6), and 4 times post-treatment (immediate, 4-weeks, 8-weeks, and 12-weeks post-treatment).

Sample size rationale

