differences between treatment conditions, therefore all possible pairwise comparisons will be conducted rather than an omnibus test. The slope by treatment condition interaction will be the effect of interest in determining whether there is differential learning or forgetting across low, mid, high testing. While the focus of our analyses is on treated words, a similar modeling approach will be used to model any learning of control words during treatment. We expect relatively flat trajectories for control words in all three treatment conditions and this will allow for inferences to be made about the effect of treatment rather than development or maturation Research Question 3.2: We will add pre-treatment measures as covariates to the models used in RQ3.1 to examine the relationship between these covariates and (a) learning slopes during treatment and (b) forgetting slopes post-treatment. Recall that there are several skills relevant for learning (language, attention, working memory, episodic learning) and forgetting (treatment learning, decay) and that we have multiple measures to tap different aspects of each skill (see measured variables table). Likewise, we also will examine biological and environmental variables as predictors. Previous research has indicated that the test measures are moderately correlated at around  $r = .50$ . Since these measures are theoretically and mathematically distinct (which we will confirm via correlations), we will examine the effect of each of these predictors individually. We hypothesize that higher language, attention, working memory, and/or episodic learning scores will be associated with steeper slopes during treatment. Similarly, we hypothesize that better treatment learning and decay scores will be associated with smaller slopes, indicating less decline post-treatment. These hypotheses are consistent with theories of learning and forgetting. However, it is likely that not all of these covariates will be significantly related to performance. Research Question 3.3: We will classify responses at the end of treatment (learner vs. non-learner) and post-treatment (rememberer vs. forgetter). Then, earlier performance will be analyzed to determine when treatment and post-treatment outcomes can be predicted. This yields empirically based benchmarks for progress and an understanding of the stability of learning and forgetting over time. As with RQ 3.1 and 3.2, we will separate treatment and post-treatment data as well as definition and naming data. Within each dataset, we will classify each child as having a negative or positive outcome based on performance at the last point in the series (i.e., reading 6 for treatment, 12-month post for post-treatment). We will use the accuracy range for the untreated control words to determine the cut-offs for this classification. Then, we will select an appropriate cut-off score at each earlier point during treatment or post-treatment. Because we have decided that the cost of false positives is greater than that of false negatives (see progress report), we will select cutoffs that minimize false positives. At each test point, measures of sensitivity, specificity, and positive/negative likelihood ratios and predictive values will be calculated. We will then determine the earliest point when we can accurately predict treatment and post-treatment outcomes

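### H3.3 predicts a step-by-step rise in predictive accuracy, but the plan compares nothing across points, and with 60 children its cut-off-based estimates are too noisy to show such a rise even when it is real

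*Combined protocol and SAP*

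**What the plan says.** Hypotheses, 3.3(a): "Accuracy in predicting learning outcomes will increase at each treatment point". Hypotheses, 3.3(b): "Accuracy in predicting retention outcomes will increase at each post-treatment point". The candidate points are readings 1 to 5 during treatment, and the immediate, 4-week and 8-week tests afterwards.

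Statistical models, Research Question 3.3, holds the only analysis. Each child is classed as having a positive or negative outcome at the last point of the series, using the range of accuracy on control words. Next, "we will select an appropriate cut-off score at each earlier point during treatment or post-treatment", chosen to keep false positives low because the investigators regard them as the costlier error. Then: "At each test point, measures of sensitivity, specificity, and positive/negative likelihood ratios and predictive values will be calculated". The stated end product is the earliest point at which prediction is accurate. Definition and naming data, and treatment and post-treatment data, are handled separately.

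No other section fills the gap. Inference criteria covers likelihood ratio tests for the growth models. Follow-up analyses adds only subgroup analyses for this question. Sample size rationale says that this question has no power analysis.

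**The concern.** H3.3 is a directional statement about one quantity, but the plan supplies six and does not say which is accuracy. With four datasets (definition and naming, during and after treatment) that makes 4 × 6 = 24 series, with no interval, paired comparison or trend test for any of them.

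All six measures depend on a cut-off chosen afresh at each point. A rule that limits false positives holds specificity near its ceiling, so any visible change falls on sensitivity. Sensitivity then depends on where the few highest-scoring non-learners happen to fall.

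Two errors become possible. A true H3.3 could be rejected because an estimate dips at one reading. Or the team could choose, after seeing the results, whichever measure happens to rise. The earliest-point benchmark, which is the practical output, is read from the same unstable estimates.

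**Working it through.** The documents give no figure for Research Question 3.3, so there is none to reproduce.

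**Inputs from the documents.** Sample size: "Sixty kindergarten children with DLD will participate". Scores run from 0 to 30, from "30 treated words and 30 control words". There are five treatment and three post-treatment prediction points. Intraclass correlations (ICC) are .10 and .30 (Sample size rationale).

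**Inputs assumed.** The control-word range and the specificity target are not given. The outcome cut-off, the cut-off rule, the mean scores and the correlation of each point with the last are therefore assumptions.

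**Step 1: rough size of the noise.** In one large simulated population 38% of children are learners, so 60 × .38 = 22.8 learners. The binomial standard error of sensitivity is √[s(1 − s)/22.8]. At s = .44 it is √(.2464/22.8) = .10. In a five-point scenario run on 60,000 children, true sensitivity is .24, .27, .44, .51, .60 (AUC rises from .64 to .87). The steps are .03, .17, .07 and .09. If the learner share is similar, three of the four steps are smaller than the standard error of a single estimate, before any allowance for choosing the cut-off.

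**Step 2: zero-false-positive cut-off.** 60 children, logistic growth, learner = at least 6 of 30 words at reading 6, cut-off = highest non-learner score + 1; three settings, 4,000 trials each. Mean AUC rises from about .71 at reading 1 to .94-.96 at reading 5. Sensitivity rises at all four steps in 23-30% of trials, so it fails in 70-77%. AUC rises at all four in 52-61%, so it fails in 39-48%. The between-trial SD is .11-.16 for sensitivity and .02-.07 for AUC.

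**Step 3: a different model.** Latent ability is a Markov Gaussian series whose correlation with the last point rises, and scores are Binomial(30, p) on a logit scale. The between-child SD is √[ICC/(1 − ICC) × π²/3], which is .60 at ICC .10 and 1.19 at ICC .30. In the table the cut-off gives the best sensitivity with specificity at least .90, and a positive outcome is at least 8 of 30. There are 400 runs at N = 60, so the Monte Carlo standard error is at most √(.25/400) = .025. There are 150 runs at N = 600, run for ICC .30 only. Entries in the Fails columns are the proportion of runs without a strict rise at every step.

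| Series, ICC, correlations | Fails, sensitivity, N=60 | Fails, AUC, N=60 | Last > first, sensitivity / AUC, N=60 | Fails, sensitivity / AUC, N=600 |
|---|---|---|---|---|
| Treatment, .10, .4-.9 | .92 | .84 | .90 / .97 | – |
| Treatment, .10, .75-.97 | .96 | .91 | .85 / .92 | – |
| Treatment, .10, .2-.95 | .87 | .71 | .98 / 1.00 | – |
| Treatment, .30, .4-.9 | .78 | .56 | .99 / 1.00 | .20 / .01 |
| Treatment, .30, .75-.97 | .91 | .72 | .96 / .99 | .35 / .03 |
| Treatment, .30, .2-.95 | .72 | .39 | 1.00 / 1.00 | .04 / .01 |
| Post, .10, .7-.9 | .74 | .58 | .70 / .79 | – |
| Post, .10, .5-.95 | .54 | .29 | .90 / .97 | – |
| Post, .30, .7-.9 | .55 | .35 | .85 / .93 | .06 / .00 |
| Post, .30, .5-.95 | .26 | .07 | .98 / 1.00 | .00 / .00 |

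Ties do not explain the failures. With SD 1.0 and the specificity .90 rule, true reversals of sensitivity alone occur in 60-91% of five-point series. Across the runs, specificity rises strictly at every step in only 0-4%.

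**Step 4: what drives it.** In the three ICC .30 treatment rows, going from 60 to 600 children cuts the sensitivity failure rate by .78 − .20 = .58, .91 − .35 = .56 and .72 − .04 = .68. Switching to AUC at N = 60 cuts it by .78 − .56 = .22, .91 − .72 = .19 and .72 − .39 = .33. Sampling error is the larger part. The comparison with AUC does not separate the cost of using a cut-off at all from the cost of re-choosing it.

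**Step 5: a further check** at N = 60, also on assumed inputs. Sensitivity fails in 80-97% of five-point and 27-79% of three-point series, and AUC fails in 59-90% of five-point series. The signal-to-noise ratio of an AUC trend is about 1.1-1.5 times that of a sensitivity trend under the specificity .90 rule, and 1.5-2.0 times under the zero-false-positive rule.

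**The case against.** The strongest reply is that the plan's measures are sound and merely imprecise. If the rule holds specificity roughly constant, sensitivity is being compared at about matched specificity, which is a fair comparison. Re-choosing the cut-off is also sensible, because scores are expected to climb across readings and one fixed cut-off would mix growth with accuracy. At 60,000 children, true sensitivity rose at every point in every false-positive-limiting scenario examined. This stands. A reader might infer that the plan cannot answer H3.3 with its own measures, but that goes too far.

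A reader might also infer that the cut-offs are the cause and that AUC cures the problem. Steps 2 to 5 do not support this, since AUC often fails the every-step criterion too.

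Nor does the plan say that H3.3 will be assessed by strict increases in the sample estimates. The hypothesis wording invites that reading, and the plan offers no other criterion. The stated decision is the earliest accurate point.

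Finally, full AUC averages over cut-offs with many false positives, which the investigators have said they want to avoid. That is a real, if small, cost.

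**Conclusion.** The point holds in a limited form. H3.3 has no designated accuracy measure and no comparison across points. With 60 children, sensitivity at a re-chosen, false-positive-limiting cut-off should not be expected to rise step by step even when the truth does. Over all the simulations, it fails in about 70-97% of five-point treatment series and about 26-79% of three-point post-treatment series.

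The treatment result held in every scenario tried. A reader might extend it to say that the post-treatment series would usually stall as well. That is not secure: with a steep true rise and ICC .30, only 26% fail.

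The percentages rest on assumed mean scores, correlations, outcome cut-offs and cut-off rules, and are not figures from the documents. The direction did not depend on any one model or rule. Much of the gain comes from replacing the every-step criterion with one contrast. In the table, a first-versus-last contrast has the right sign in 85-100% (sensitivity) or 92-100% (AUC) of treatment runs, and in 70-98% or 79-100% of post-treatment runs. AUC adds a further, moderate gain in precision.

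**What to change.** In Statistical models, Research Question 3.3:

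- For H3.3 only, name the AUC of the raw score at each earlier point as the accuracy measure, separately for definition and naming. That is 2 × 5 + 2 × 3 = 16 AUCs.
- Give bootstrap intervals that resample children, so that points are compared on the same children. Assess H3.3 in each series by one contrast fixed in advance, either a trend across points or last minus first, and not by strict increases at every step.
- Keep sensitivity, specificity, likelihood ratios and predictive values, with intervals, for the benchmark cut-offs and the earliest-point decision. Re-choose the cut-off within each bootstrap sample so that the intervals include that choice.
- Report sensitivity at the chosen low-false-positive cut-off beside each AUC, because full AUC also counts regions that the plan regards as costly.

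The cost is SAP wording and a few lines of code, on data that the plan already calls for. No children, visits or tests are added, and no planned statistic is lost. The change does not by itself remove the noise from the earliest-point decision, but the intervals will show how large that noise is.

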#### Transformations

One of the primary dependent variables is a count of the number of words correct which will not fit a normal distribution. Rather than transforming the variable, an appropriate link function such as a Poisson distribution will be used. We will center time at the last intervention reading point for all models.

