3.1. Power Analysis for Research Question 3.1. Monte Carlo studies were conducted using Mplus to determine power to detect treatment differences in slope across 7 (treatment) or 5 (retention) data points. Slope reliabilities of .6 and .8 were considered in the specification of the population parameters. Both linear growth models and latent basis models with nonlinear growth were examined given that the expected shape of the trajectories is uncertain. Intraclass Correlation Coefficients (ICCs) from our prior studies indicated that between 10% and 30% of the variance in word learning was between persons. Thus, ICCs of both .10 and .30 were used in the power analysis. We will have .80 power or greater to detect moderate slope differences ( $d = .5$ ) between two groups of 20 individuals in the treatment phase with 7 data points. In the post-treatment phase, with 5 data points, we will have .80 power to detect slightly larger slope differences ( $d = .6$ ). Attrition has been minimal (1.9%). Thus, we will recruit additional children, as needed, to replace any children who do not complete the study. We will check the assumptions used in our power analysis yearly and update target sample size to maintain power. 3.2. Power Analysis for Research Question 3.2. Additional Monte Carlo studies were conducted using the same software, intraclass correlation coefficients, and slope reliabilities as for RQ3.1. Prior research by the team has indicated that correlations between predictors and learning are in the range of .4 and .5. Power to detect the relationship between level two predictors of this magnitude and slopes added to the treatment model will range from .70 to .85. Power to detect the main effect of each covariate at the last treatment point will similarly range from .73 to .87. Although power appears sufficient with a sample size of 60, an alternative approach if power is insufficient is to loosen our criteria for statistical significance and search for “promising” key moderators. Promising key moderators would need further testing as the

development of this treatment moves forward but would inform our understanding of which children with DLD may benefit from the treatment, addressing the research question. 3.3 There is no specific power analysis for research question 3.3.

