### Randomization

Random assignment to the three treatment condition occurs at the participant level. Participants will also be randomly assigned to one of two treated word lists within each treatment condition.

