## Analysis Plan

### Statistical models

Research Question 3.1: We will use a multi-level modeling approach for (a) learning during treatment (7 observations: pre-treatment, repeated readings 1-6); (b) post-treatment forgetting (5 observations: reading 6, immediate, 4-week, 8-week, 12-week post). We will examine definition and naming data separately, yielding four models: treatment definition, treatment naming, post-treatment definition, post-treatment naming. For each model, observations at each test (level 1) are available for each participant (level 2). The expected shape of the trajectories is not known so the analytic approach will use either linear growth modeling or latent basis modeling, depending on which is most appropriate. Participants are randomly assigned to treatment (low, mid, high testing), and treatment will be included in the model as a fixed factor at level 2. The dependent variable is number of words correct. This count variable will likely not fit a normal distribution, and thus, an appropriate link function, such as a Poisson distribution, will be used. The research aim is to detect

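### The treatment-phase models let randomised arms start at different pre-treatment levels, which costs precision for the learning-slope contrast; reading-6 centring becomes unsafe if condition terms can be tested out

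*Combined protocol and SAP*

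**What the plan says.** Randomisation is individual: "Random assignment to the three treatment condition occurs at the participant level" (Randomization), "yielding 20 children per treatment condition" (Sample size).

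Under Statistical models, Research Question 3.1, the treatment-phase series is "a) learning during treatment (7 observations: pre-treatment, repeated readings 1-6", so the pre-treatment count is itself an outcome. In that model "treatment will be included in the model as a fixed factor at level 2". For inference, "The slope by treatment condition interaction will be the effect of interest", and "all possible pairwise comparisons will be conducted rather than an omnibus test". There is one such model for definitions and one for naming.

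Transformations adds: "We will center time at the last intervention reading point for all models". Inference criteria lets likelihood ratio tests decide which fixed and random effects the growth models need, and also uses them to judge the treatment effects.

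No section holds the arms equal at pre-treatment or adjusts Research Question 3.1 for the pre-treatment word count. The covariates of Research Question 3.2 come in later, one at a time. Read plainly, each arm has a free level and a free slope.

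**The concern.** Because children are randomised and the first score precedes treatment, the true pre-treatment means of the three arms are equal. A model with a free level for each arm does not use this. Within a child, the errors of the fitted start and the fitted slope are negatively correlated. An arm whose early scores happen to be low through test noise therefore gets a fitted line that is somewhat too steep. Hypothesis 3.1a rests on slope differences between arms of 20, so avoidable noise in that contrast matters.

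There is a second, separate risk. With time zero at reading 6, the condition main effect is the difference between arms at the end of treatment. If a likelihood ratio test removes that term and condition by time stays, the model makes the arms meet at the point where differential learning should be largest.

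**Working it through.** **Inputs from the plan.** Seven occasions, coded t = 0 (pre-treatment) to 6; 20 children per arm; pairwise slope contrasts; ICC .10 or .30 and slope reliability .6 or .8 (Sample size rationale).

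**Assumptions.** Linear growth, equal spacing, normal errors, ICC read as the between-child share of variance at pre-treatment, two-sided .05. The correlation r between a child's true start and true slope is not stated; 0 is used first, then -.3 to +.5.

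**1. The plan's own figure.** The rationale gives power of .80 or more at d = .5 "between two groups of 20 individuals in the treatment phase with 7 data points". A plain two-group calculation gives .35 (two-sided .05) or .47 (one-sided). With d in true-slope SDs it gives .23 or .29. With d in total SDs over the whole phase it gives .10 to .18, and per reading .98 to 1.00. None is near .80. Alpha, the metric of d and the population values are not given, so this does not show that .80 is wrong. Below, .80 is only a reference point.

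**2. Variance of a child's fitted start and slope.** Scale the between-child start variance to 1. Then residual variance s² = (1 - ICC)/ICC = 9 or 2.333, and slope variance g = [rel/(1 - rel)] × s²/28. For t = 0 to 6, least squares gives start variance .4643, slope variance 1/28 = .0357 and covariance -.1071, each times s². So:

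- V00 = 1 + .4643 s²
- V01 = -.1071 s² + r√g
- V11 = g + s²/28

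**3. Free against shared start.** The variance of a pairwise slope contrast is (2/20)V11 with free starts and (2/20)(V11 - V01²/V00) with a shared start. The fraction saved is R = V01²/(V00·V11). The equivalent gain in children is 1/(1 - R) - 1. Power of .80 becomes Φ(2.802/√(1 - R) - 1.960). At r = 0:

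| ICC | Reliability | V00 | V01 | V11 | R | Gain | .80 becomes |
|---|---|---|---|---|---|---|---|
| .10 | .6 | 5.179 | -.964 | .804 | .223 | 29% | .89 |
| .10 | .8 | 5.179 | -.964 | 1.607 | .112 | 13% | .84 |
| .30 | .6 | 2.083 | -.250 | .208 | .144 | 17% | .86 |
| .30 | .8 | 2.083 | -.250 | .417 | .072 | 8% | .83 |

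Gains at other r, in the same row order:

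- r = -.3: 49%, 26%, 41%, 26% (power .88 to .93)
- r = +.3: 16%, 5%, 5%, 0.7% (power .803 to .855)
- r = +.5: 10%, 2%, 1%, 0.2% (power .801 to .836)

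**4. Simulation check** (1,500 trials of 60 children, first and last rows, r = 0). The ratio of shared to free variance was .77 and .94, against .78 and .93 by formula. With the condition main effect kept, moving time zero from pre-treatment to reading 6 left the slope contrast unchanged to within 1e-13. The free-model contrast was uncorrelated with the true chance difference in starting ability (.02 and -.00), but correlated with the observed pre-treatment difference (-.36 and -.15). In a separate simulation, type I error stayed at .048 to .052.

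**5. Dropping the condition main effect under reading-6 centring.** A true slope difference of 1 is then estimated as 1 - 6·C/V66, with C = V01 + 6V11 and V66 = V00 + 12V01 + 36V11. For the first row, C = 3.857 and V66 = 22.536, so the estimate is 1 - 23.14/22.54 = -.03. The other rows give -.01, .09 and .04. This need not be rare. Where the slope test has .80 power, a pairwise test of the reading-6 difference is non-significant with probability 1 - Φ(6 × 2.802 × √(V11/V66) - 1.960), which is .11 to .18 over the four rows.

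**The case against.** A growth model with free intercepts by arm is standard and valid. Its slope contrast is unbiased, and no type I error problem is shown. That stands: the issue is efficiency.

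The start-slope correlation may well be positive. Hypothesis 3.2a expects children with better language to learn faster, and the rationale cites predictor-learning correlations of .4 to .5. Those are different measures from the pre-treatment word count, so this is only suggestive. If it is right, though, the gain is at most 5% in three of the four rows from r = +.3 upwards.

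The shared start leans on the growth shape, which the plan says is unknown. Take one arm linear from 1 to 8 words and another following 1 + 7√(t/6), so that both ends agree. The free linear model gives a slope difference of -.105 and a fitted start difference of 1.236. The shared-start model gives -.105 + (.964/5.179)(1.236) = +.13 at ICC .10, or +.04 at ICC .30. Both models are wrong at reading 6, where the true difference is 0: the free model gives 1.236 - 6(.105) = .6 words and the shared one about .8 or .3. So the objection calls for a shape check but does not favour the free start.

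Many analysts would never drop a main effect while keeping its interaction. The plan does not say so, and that protection should be written down.

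A reader might infer three stronger things that the documents do not support. First, that reading-6 centring causes the loss: with the main effect kept it only reparameterises the model. Second, that real chance imbalance in ability turns into slope differences: the level term absorbs it, and only early-score noise leaks in. Third, that the gain is large because counts are modelled: a linearised Poisson version gave variance reductions of 10% to 67%, but on assumed means (0.5 to 2 words rising to 6 to 15) that appear nowhere in the plan.

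**Conclusion.** The point holds as a loss of efficiency for Hypothesis 3.1a. It shows neither bias nor invalid inference. At zero start-slope correlation, a shared pre-treatment mean removes about 7% to 22% of the slope-contrast variance. The benefit is larger if weak starters learn faster and shrinks towards nothing if strong starters do. These sizes rest on linear growth, normal errors and the stated reading of the ICC. They are relative gains and do not certify the plan's .80.

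The centring rule matters only together with the open-ended selection of fixed effects. That combination permits a model in which a true slope difference nearly vanishes. The plan does not commit to such a model, but nothing in it rules one out.

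**What to change.** For the treatment-phase definition and naming models:

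- Set time zero at pre-treatment (latent-basis loading 0 there).
- Include time and condition by time, with no condition main effect, so the arms share one pre-treatment mean.
- Keep the child random intercept and slope.
- Derive reading-6 contrasts from this model: 6 times the slope difference, or the reading-6 loading times the difference, on the scale of the chosen link.
- Check fit at pre-treatment in each arm, and use the latent basis form if the linear one misfits.
- Report the free-start model as a sensitivity analysis.

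In Inference criteria, state that condition terms are fixed in advance and are neither added nor dropped by testing. In the post-treatment models keep reading-6 centring with a free condition level, because by then the arms may truly differ.

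The cost is about a sentence each in Statistical models, Transformations and Inference criteria, plus a changed model statement. No extra data or children are needed. The one small downside is the reliance on growth shape, which the fit check and the sensitivity analysis address.
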